### 2.6.5 Post-Discharge

Post-discharge care is not altered for purposes of this study. Both groups in both cohorts will receive standard of care post-discharge analgesics as determined by their treating surgeon. These include NSAIDs and opioids (oxycodone, oxycodone+acetaminophen (Percocet, Tylox), hydrocodone+acetaminophen (Norco, Vicodin), tramadol, and codeine+acetaminophen (Tylenol#3)). Selection and quantity of opioids dispensed will be at surgeons' discretion.

Opioids will be dispensed in a medication monitoring system, to measure drug utilization during the 30d post-discharge follow-up period. After discharge, patients record their pain self-assessments, home opioid use, and side effects each day through emailed REDCap or paper surveys, allowing real time data recording. Additional REDCap surveys will be emailed at 6 and 12 mo.

For approximately 30d postop, patients will be queried once daily (evening) regarding pain (average at rest, with activity, with coughing, using NRS), pain relief and pain interference with eight activities of daily living (5-point Likert scale) using the NIH PROMIS Pain Intensity 3A and Pain Interference 6A questionnaires. Recovery is assessed using the QoR-15. Patients also record opioid and non-opioid analgesic use, sedation, and time to return to work and ADLs, and opioid side effects (ORSDS). This electronic-based system has improved daily data capture, improved reliability, and can trigger patient contact if necessary to ensure maximal data capture.

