### 2.6.7 Observations and Measurements

All assessment scales are the standard in perioperative methodology, and are conducted by a trained member of the research team, blinded to randomization allocation. Assessments are conducted after PACU admission, every 15 min for the first hour, hourly for the next 4 hr, at bedtime, and ~24 hr after surgery or prior to hospital discharge (whichever is first), using established protocols. We use the standard, well-defined, reliable, recommended patient-reported outcome measures to assess pain. Pain intensity is assessed (at rest/while coughing/with activity) using the validated 0-10 Numeric Rating Scale (NRS). Pain relief is assessed using the standard 5 point scale (none=0, slight=1, moderate=2, good=3, complete=4). Observed sedation (Modified Observer's Assessment of Alertness/Sedation, MOAA/S) and subject's self-assessment of sedation are recorded concurrently with pain assessments. Opioid side effects are assessed prior to discharge using the Opioid-Related Symptom Distress Scale (ORSDS). ORSDS uses 4-point Likert scales to characterize 12 opioid side effects (nausea, vomiting, constipation, difficulty urinating, difficulty concentrating, drowsiness, dizziness, confusion, fatigue, itchiness, dry mouth, and headache) according to frequency, severity, and bothersomeness. Twelve symptom-specific ORSDS scores (0-4) are the average of the 3 distress dimensions (frequency, severity, and bothersomeness). The composite ORSDS (0-4) is the mean of the 12 individual scores. ORSDS has both construct reliability and content validity. Drug administration for prophylaxis/treatment of opioid side effects (e.g. antiemetics) during hospitalization is recorded from the electronic medical record. Particular attention will be paid to opioid-related adverse events, most importantly respiratory depression. During PACU recovery, four types of respiratory-specific events will be assessed:

1. Hypoventilation (3 episodes of <8 respirations/min)
2. Apnea (episode of apnea  $\geq 10$  seconds)
3. Hypoxemia (3 episodes of oxyhemoglobin saturation  $<90\%$  for 30 sec with/without nasal oxygen)
4. "Pain/sedation mismatch" (defined as MOAA/S 0-2 and a numeric pain score  $> 5$ )

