### 2.6.8 Primary and secondary outcome measures

Primary outcome measure: Total 30d post-discharge home opioid use (number of tablets). This is because surgeons prescribe a variety of post-op opioids (oxycodone, tramadol, oxycodone+acetaminophen, hydrocodone+acetaminophen, codeine+acetaminophen), we avoid any confounding by use of opioid conversion tables, and the most important factor in opioid diversion and misuse is the number of left-over tablets.

Secondary outcome measures:

1. Total 7d post-discharge home opioid use (number of tablets).
2. Total intraoperative non-methadone opioid administration
3. Total PACU opioid administration
4. Total hospital non-methadone opioid administration

Exploratory outcomes:

1. Total day of surgery nonmethadone IV opioid administration
2. Total day of surgery nonmethadone IV and oral opioid administration
3. Total day of surgery opioid administration
4. Postoperative day 1 total IV oral and opioid administration (for short-stay cohort only)
5. Total hospital opioid administration
6. PACU pain scores (NRS) and pain relief score; at time-specific intervals
7. Duration of intraoperative analgesia (median time to request for re-medication with opioid)
8. PACU side effects and adverse events: respiratory depression (4 events occurrence per above), sedation (MOAA/S score), nausea/vomiting (number of events); at time-specific intervals and total
9. PACU duration of stay
10. 7d and 30d total post-discharge home opioid use (in morphine equivalents)
11. 7d and 30d post-discharge pain scores (NRS) and pain relief score; daily
12. Total pain relief (TOTPAR), calculated as the area under the curve of pain relief score vs time
13. 7d and 30d post-discharge opioid side effects (ORSDS); daily, weekly and total (summed and average)
14. Time to cessation of post-discharge opioid use
15. 7d and 30d post-discharge unused opioid tablet count
16. Quality of recovery at 7d, 14d, 21s, 30d, 6 mo, and/or 12 mo (VR-12, Barthel index, QoR-15, functional independence, return to work)
17. Surgeons' opioid prescribing patterns

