### 2.8 Hypothesis testing

For all Aims, the two cohorts ("short-stay" and "same-day" surgery) are analyzed separately. Subgroup analysis may also explore specific surgical procedures (procedure-specific analgesia).

Aim 1: Compare the influence of methadone vs short-duration opioids on short-term (before discharge) and intermediate term (1-30d post-discharge) opioid consumption.

30d post-discharge opioid use ( $> 5$  pills) will be compared between arms using Chi-square tests and multiple logistic regression, with opioid group as a predictor and adjusting for the important clinical and demographic covariates. Total pill consumption will be compared using GEE model with Poisson link function. In addition, a time-to-event (survival) model will be fit to compare time to opioid discontinuation between the two groups.

adjusting for the appropriate covariates. Opioid use during intraop, in-hospital post-op, and post-discharge periods will be evaluated using appropriate model and data transformation, depending on the distribution of the data. It is common in some analgesic trials that subjects dropping from different treatment groups differ with respect to reasons for early discontinuation (i.e. not random but outcome-related). Therefore analysis will not be “completers only”. Drop-out rates will be compared between the drug groups, and 30d opioid consumption ( $>5$  vs  $\leq 5$  pills) analyzed with and without drop-outs. Drop-outs will be censored at the time of dropping out in time to discontinuation analysis. A corollary of opioid consumption by patients is opioid prescribing by surgeons. It is possible that surgeons’ prescribing practices (# tablets per patient) may change during the study (coincidentally or as a result thereof) and this will be explored.

**Aim 2:** Compare methadone vs short-duration opioids in reducing short-term (immediate postoperative), intermediate term (1-30d post-discharge), and chronic (6-12 mo) postoperative pain.

Pain reduction effectiveness of methadone vs short-duration opioids will be compared using repeated measures models to adjust for multiple measures on each subject. Depending on the distribution of NRS, VAS and pain relief data, data will be analyzed as normal, or transformed into an ordinal or other scale.

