**Aim 3:** Evaluate major and bothersome short-term (before discharge) and intermediate term (1-30d post-discharge) opioid-related side effects with methadone vs short-duration opioids.

Side effects (respiratory-specific events, composite ORSDS) will be compared between the groups using Chi-squared or Fisher exact test, as appropriate, and using logistic models to adjust for important clinical and demographic covariates.

**Aim 4:** Compare overall recovery after surgery/anesthesia with methadone vs short-duration opioids, as defined by changes in reported Health-related Quality of Life, functional independence, and ability to return to work and normal activity.

Overall recovery will be assessed using chi-square tests for categorical outcomes and t-tests for continuous outcomes as well as a repeated measures model to adjust for multiple time points.

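### Aim 3 sends the composite ORSDS, a 0–4 average of 36 ratings, to chi-square/Fisher tests without defining any categories (exploratory outcome 13)

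*Combined protocol and SAP*

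**What the plan says.** Section 2.6.7 builds the score in two steps: "Twelve symptom-specific ORSDS scores (0-4) are the average of the 3 distress dimensions (frequency, severity, and bothersomeness"), and then "The composite ORSDS (0-4) is the mean of the 12 individual scores". The same section also describes the items as 4-point Likert scales.

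The score is collected in hospital ("Opioid side effects are assessed prior to discharge using the Opioid-Related Symptom Distress Scale (ORSDS")) and daily after discharge (section 2.6.5: "Patients also record opioid and non-opioid analgesic use, sedation, and time to return to work and ADLs, and opioid side effects (ORSDS")). In section 2.6.8, exploratory outcome 13 is "7d and 30d post-discharge opioid side effects (ORSDS); daily, weekly and total (summed and average"). The pre-discharge ORSDS is not itself in the outcome list.

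For the analysis, section 2.8, Aim 3, says: "Side effects (respiratory-specific events, composite ORSDS) will be compared between the groups using Chi-squared or Fisher exact test, as appropriate", followed by "using logistic models to adjust for important clinical and demographic covariates". The Synopsis gives the same two tests for side effects in general and does not name the ORSDS.

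The neighbouring aims are treated differently. Aim 2 gives pain a repeated measures model and a rule for the scale: depending on the distribution, "data will be analyzed as normal, or transformed into an ordinal or other scale". Aim 4 separates categorical from continuous outcomes.

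**The concern.** Chi-square and Fisher tests compare counts in categories. Respiratory-specific events are categories already; an average of 36 ratings is not. The closing words of the Aim 3 test sentence choose between the two tests and do not supply a cut-point. The logistic model does not settle the matter either: an ordinal model takes the score uncut and a binary model does not, and the plan does not say which is meant.

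Two things are at stake. A cut-point left open can be chosen after the data are seen. And if the arms differ by a general shift, splitting the score discards information. The trial's hypothesis (section 2.3) includes side effects that are no worse or fewer, and the ORSDS is the only post-discharge side-effect measure that Aim 3 names. A low-powered comparison is more likely to give a null result, and a null result may be read as similarity.

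**Working it through.** **Plan's own figure.** The documents give no effect size, SD, distribution or threshold for the ORSDS. The only sample size is for the primary outcome (section 2.7): 150 per group. It reproduces with 45% against 0.65 × 45% = 29.25%, two-sided 5%, 80% power, mean proportion 0.37125:

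n = [1.96·√(2 × 0.37125 × 0.62875) + 0.842·√(0.45 × 0.55 + 0.2925 × 0.7075)]² / 0.1575² = 147 per group.

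It is used here only as the number of patients available per arm.

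**How fine the score is.** 12 symptoms × 3 dimensions = 36 ratings. Scored 0–4 in whole numbers, the sum runs 0–144, so 145 values. With four levels per item, 36 × 3 + 1 = 109 values. Both are close to continuous. In simulated 36-item composites (150 per arm, two assumed symptom levels), 300 patients showed about 57–91 distinct values. Cross-tabulated uncut, 83–99% of cells had expected counts below 5, and chi-square had 3–8% power for shifts of 0.32 and 0.40 in the underlying severity. So categories are needed in practice.

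**Power for a general shift.** Assumed: 0.33 SD, normal scores, one summary per patient, 150 per arm, two-sided 5%.

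- *t-test:* noncentrality 0.33 × √(150/2) = 2.858, power 81%.
- *Rank test:* the probability that a patient in one arm outscores one in the other is Φ(0.33/√2) = 0.592. Power ≈ Φ(√(12 × 150²/301) × 0.0923 − 1.96) = Φ(0.80) = 79%. Simulation gives 79–80%.
- *Median split:* proportions above the cut are Φ(±0.165) = 0.566 and 0.434. Power = Φ[(0.1311 − 1.96 × 0.05774)/0.05724] = Φ(0.313) = 62%. Matching the t-test would take about 236 per arm.
- *Higher cuts,* same two-proportion formula, shift down or up:

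| Controls above cut | Methadone above cut | Power |
|---|---|---|
| 10% | 5.4% or 17.1% | 33% or 43% |
| 20% | 12.1% or 30.4% | 46% or 55% |

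A monotone transformation leaves the rank test and the median split unchanged but not the t-test. With log-normal scores (skew about 6) the t-test falls to about 61%. With a floor at zero and a skewed tail (40–80% of controls above zero) it has 46–71%, against 63–79% for the rank test. A raw mean comparison is therefore not a safe default.

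**Power when only the severe tail differs.** Assumed: same bulk, different fraction above a severe cut, 150 per arm, simulated.

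| Above severe cut | Chi-square at that cut | Rank test |
|---|---|---|
| 10% vs 2% | about 87% | 21–23% |
| 15% vs 5% | about 84% | about 30% |
| 20% vs 8% | about 86% | about 44% |

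Here the ordering reverses.

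**Aim 4, baseline adjustment.** With equal variances before and after, and correlation ρ, the variance is σ² for post scores, 2(1 − ρ)σ² for change scores and (1 − ρ²)σ² for ANCOVA. The reductions from ANCOVA are ρ² and (1 − ρ)/2 respectively. At ρ = 0.3, 0.5 and 0.7 that is 9%, 25% and 49% against post scores, and 35%, 25% and 15% against change scores.

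**The case against.** The strongest reply has three parts.

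First, this is one exploratory outcome among 17, and the logistic models may already be meant as ordinal. Both points are fair. The power losses apply only where the score is actually categorised. Even so, the unadjusted test still has no categories, and the logistic phrase covers respiratory events as well, for which a binary model is natural.

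Second, a reader might infer that splitting the score always loses power. The evidence does not support that. The loss holds for shift-type differences, and the severe-tail examples go the other way. Aim 3 speaks of serious or troublesome effects, so the proportion of patients with marked symptoms is a legitimate question. A threshold fixed in advance would also cure the defect and keep the planned tests. What is missing is the threshold.

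Third, a reader might infer that Aim 4 has the same fault. It does not. It describes recovery in terms of change, section 2.6.7 anticipates comparing postoperative with preoperative values, and t-tests with a repeated measures model are valid after randomisation. Baseline adjustment there is an improvement in precision, not a correction.

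**Conclusion.** The specification gap stands: the tests named for the composite ORSDS need categories that the plan does not give. It affects exploratory outcome 13 and the unlisted pre-discharge ORSDS. The primary and secondary outcomes and the sample size are untouched, and chi-square/Fisher remains suitable for respiratory-specific events. Nothing in the documents supports reading this as a flaw in the trial's main conclusion.

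The cost is conditional. For a general shift, a split gives about 62% at best among the cuts worked above, against about 79% for a rank test; for a difference confined to the severe tail, a pre-specified severe cut is better. Apart from 150 per arm, every input to these figures (effect size, distribution, one summary per patient) is assumed, so they show direction and rough size only. The point that needs no assumption is that the cut-point is open and should be closed before unblinding.

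**What to change.** Before unblinding, amend Aim 3 as follows.

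- Compare each patient's 7-day and 30-day average composite ORSDS, and the pre-discharge ORSDS, by a Wilcoxon rank-sum test.
- Use a proportional-odds (ordinal logistic) model for the covariate adjustment already planned, and state that logistic means ordinal for the ORSDS and binary for respiratory-specific events.
- Analyse the daily scores with an ordinal repeated measures model (arm, day, arm-by-day) as support, and report the weekly and summed results that outcome 13 lists alongside.
- If the proportion with major symptoms is also of interest, fix one ORSDS threshold in advance and apply chi-square/Fisher to that binary outcome. Keep those tests for respiratory-specific events.
- State the item scoring, so that the 4-point items and the 0–4 range agree, and bring the Synopsis sentence into line.

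As a free improvement for Aim 4, include the same instrument's preoperative score as a covariate for VR-12, Barthel, QoR-15, PROMIS-29 and PROMIS Global Health, all collected at baseline. This cannot apply to PROMIS Pain Intensity 3A or Pain Interference 6A, for which the survey schedule shows no baseline.

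The cost is wording only, with no new data or visits. The downside is that a common odds ratio is harder to read than a percentage, and the proportional-odds assumption must be checked.

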#### **4.3 Potential Risks**

Risks of being in this study are not materially different from those of surgery and anesthesia in general. Clinical opioid side effects are expected to be no different between the various opioids administered during and after anesthesia. The most common side effect of intraoperative and postoperative opioids such as methadone, fentanyl, hydromorphone and morphine is mild sedation, the magnitude of which is not different between the various opioids to be used, at the expected doses. The most common adverse effect of opioids is nausea and/or vomiting, which is not different between the various opioids to be used. Postoperative nausea and/or vomiting are also influenced by other drugs used intraoperatively. Respiratory depression is a potential concern with all opioids, but has not been problematic or different between opioids at the doses of methadone that have been used in similar previous studies, and not materially different than that from morphine, fentanyl and hydromorphone. Clinical data are collected for all enrolled patients, so there is also a potential risk of breach of protected health information.

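### After discharge, Aim 3 names only the 12-symptom composite ORSDS for comparison between arms, so a difference confined to one or a few symptoms could be diluted or offset

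*Combined protocol and SAP*

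**What the plan says.** Aim 3 (section 2.8) sets out to "Evaluate major and bothersome short-term (before discharge) and intermediate term (1-30d post-discharge) opioid-related side effects" with methadone versus short-duration opioids. Its analysis sentence names two endpoints: "Side effects (respiratory-specific events, composite ORSDS) will be compared between the groups", by chi-squared or Fisher exact tests and by logistic models.

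Section 2.6.7 defines the instrument at two levels: "Twelve symptom-specific ORSDS scores (0-4) are the average of the 3 distress dimensions (frequency, severity, and bothersomeness"), and "The composite ORSDS (0-4) is the mean of the 12 individual scores". The 12 symptoms include nausea, vomiting and drowsiness, alongside items such as itchiness, dry mouth and headache. The same section limits the respiratory endpoint in time: "During PACU recovery, four types of respiratory-specific events will be assessed".

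Two exploratory outcomes in section 2.6.8 bear on this:

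- Outcome 8, confined to the recovery room: "PACU side effects and adverse events: respiratory depression (4 events occurrence per above), sedation (MOAA/S score), nausea/vomiting (number of events").
- Outcome 13, after discharge: "7d and 30d post-discharge opioid side effects (ORSDS); daily, weekly and total (summed and average").

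Section 2.6.5 has patients record sedation and the ORSDS daily after discharge. Section 4.3 names mild sedation as the most common side effect, and states: "The most common adverse effect of opioids is nausea and/or vomiting". The hypothesis in section 2.3 is that methadone's side effects will be comparable to, or fewer than, those of short-duration opioids.

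**The concern.** Aim 3 covers two periods, but its named endpoints serve them unequally. In the PACU there are respiratory events, and outcome 8 lists nausea/vomiting and sedation separately. For days 1 to 30 after discharge, the one named ORSDS comparison is the composite. Outcome 13 says how ORSDS is aggregated over time but names no symptom, and no comparison between arms is stated for the daily sedation record.

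Equal weighting means that a change in nausea counts no more than a change in dry mouth. If methadone affected one or a few symptoms, the composite would show only a fraction of it. If some symptoms rose while others fell, for instance because home opioid use fell, the changes could offset each other.

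The hypothesis makes this matter. It is met by no difference as well as by improvement, so an insensitive summary favours it. Section 3.0 describes the trial as the first evaluation of methadone for outpatient anesthesia and looks to it to establish safety before wider study. Section 2.1 gives methadone a half-life of 1 to 2 days, so the first days at home are a relevant window.

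**Working it through.** **The plan's own figure.** The documents give no power, SD, correlation or effect size for ORSDS. The only power statement is for the primary outcome: 150 per arm per cohort (section 2.7). It reproduces with the unrounded control and methadone rates, 45% and 0.65 × 45% = 29.25% (147 per arm), though not with the rounded 30% (163 per arm). That is a separate matter; only n = 150 per arm is used here.

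**Inputs.** From the documents: 12 equally weighted symptom scores and 150 evaluable subjects per arm. Assumed: symptom SD 1; a difference of 0.35 in each symptom that moves; a common correlation r between symptoms; two-sided alpha 0.05; a two-sample t-test.

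**Formulas.** If k of 12 symptoms shift by 0.35:

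- composite difference = 0.35 × k/12
- composite SD = √((1 + 11r)/12), which is 0.289, 0.516, 0.599 and 0.736 at r = 0, 0.2, 0.3 and 0.5
- standardised difference d = difference / SD; power from a t-test with noncentrality d × √(150/2)

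**One symptom tested directly.** d = 0.35 gives 86% power, or 73% at alpha 0.05/3.

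**Composite.**

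| Symptoms that move | r | Difference | d | Power |
|---|---|---|---|---|
| 1 | 0.3 | 0.029 | 0.049 | 7% |
| 3 | 0 | 0.088 | 0.303 | 74% |
| 3 | 0.2 | 0.088 | 0.169 | 31% |
| 3 | 0.3 | 0.088 | 0.146 | 24% |
| 3 | 0.5 | 0.088 | 0.119 | 18% |
| 7 | 0.3 | 0.204 | 0.341 | 84% |

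**Dilution.** On the raw scale it is 12/k: 12-fold for one symptom, 4-fold for three. The composite's SD is also smaller than a single symptom's, so the standardised dilution is (12/k) × √((1 + 11r)/12). At r = 0.3 that is 12 × 0.599 = 7.2-fold for one symptom and 4 × 0.599 = 2.4-fold for three. At r = 0 the figures are 3.5 and 1.2; at r = 0.5 they are 8.8 and 2.9.

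**Cancellation.** If three symptoms rise by 0.35 and three fall by 0.35, the composite difference is (3 × 0.35 − 3 × 0.35)/12 = 0 at any correlation.

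**The reverse case.** If all 12 symptoms shift by 0.2 at r = 0.3, the composite has d = 0.2/0.599 = 0.334 and 82% power, against 41% for a single symptom.

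**The case against.** **The composite is a sound summary.** Section 2.6.7 describes the ORSDS as reliable and valid, and one score limits multiplicity. Fatigue, dizziness, confusion and difficulty concentrating could well move with drowsiness. If those four join the three named symptoms, composite power is 84% at correlation 0.3. This stands, and it is why the composite should stay.

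**Symptom-level reporting is unspecified, not excluded.** Outcome 13 refers to ORSDS without restricting it to the composite, and the synopsis says only that side effects will be compared. Sedation is recorded daily. Adverse events are described (section 4.1) and graded by CTCAE (section 4.5). This also stands. But none of these places states a comparison between arms for any symptom after discharge, so the choice of symptom would be made after the data are seen.

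**The documents predict no harm.** Section 2.2 reports no greater sedation, nausea or emesis in the pilots. Section 4.3 says nausea and vomiting do not differ between the opioids, and nothing forecasts symptoms moving in opposite directions. So cancellation is a possibility, not an expectation. Still, the absence of a difference is something this trial should be able to examine.

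**The power figures are not the plan's.** They rest on assumed inputs and a t-test, whereas Aim 3 names methods for categorical outcomes and gives no cut-off for a 0-4 score. They show the mechanism only.

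**Stronger readings to avoid.** A reader might infer that Aim 3 as a whole tests only the composite; it also names respiratory events, and outcome 8 lists PACU nausea/vomiting and sedation separately. A reader might infer a 12-fold loss for nausea, vomiting and drowsiness together; 12 is the raw-scale figure for a single symptom, and for these three it is 4, or 2.4 standardised at correlation 0.3. A reader might also infer that a real difference is bound to be reported as none. With three symptoms moving, composite power runs from 18% to 74% over the correlations shown, so the documents support only that a difference could be missed.

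**Conclusion.** The concern holds for the period after discharge. The composite is the only ORSDS measure Aim 3 names for a comparison between arms, and a difference confined to one or a few symptoms could be diluted or offset in it.

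The arithmetic of the mean needs no assumption beyond equal weights: 12-fold on the raw scale for one symptom, 4-fold for three. The loss of power depends on unknown SDs, correlations and effect sizes, and on how many symptoms move. Under the assumed inputs it is severe for one symptom (7% against 86%), moderate to large for three unless the symptoms are nearly uncorrelated, and largely absent when seven move together.

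The practical consequence lies in interpretation: a null composite would be weak support for comparable or fewer side effects. This is a gap in pre-specification that is cheap to close. It is an analysis point, and it changes no clinical management.

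**What to change.** In Aim 3 and in exploratory outcome 13:

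1. Pre-specify the differences between arms, with 95% confidence intervals, in the symptom-specific ORSDS scores for nausea, vomiting and drowsiness. Report them before discharge and over the first 7 days, in each cohort, labelled exploratory.
2. Tabulate the other nine symptom scores by arm, descriptively.
3. Keep the composite as a summary.
4. State that no conclusion of similar side effects will rest on the composite alone.

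The symptom scores are already defined and the data already collected, so no visit, questionnaire or patient is added. The cost is some analysis-plan wording and six further estimates per cohort (three symptoms × two windows). If all six were tested with a Bonferroni correction at 0.05/6, power in the illustration for each would fall from 86% to 65%. That is a reason to present them as estimates with intervals.
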